5.4.10 Adverse Event

At every visit, the Investigator or designee will question the patient about adverse events and intercurrent illnesses since the last visit, according to the National Cancer Institute (NCI) Common Terminology Criteria for Adverse Events (CTCAE) Version 4.03 for AE grading, and will record the pertinent information on the CRF.

From the time the study Informed Consent is signed through the day of study drug administration, only SAEs that are related to study procedures are to be recorded. For all non-Target population patients, all adverse events from the time of study drug administration until Day 35 (± 5 days) post-TURBT will be recorded. For Target population patients, all adverse events will be recorded from the time of study drug administration until the 3-month Follow-up Visit. Only deaths and AEs related to study procedures will be recorded from the 3 month visit until the End-of-Study.

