1.3.2 Clinical Safety of Qapzola

The majority of data establishing the safety of a single intravesical instillation of Qapzola in the post-TURBT setting came from the two placebo-controlled pivotal studies, SPI-611 and SPI-612 (N=808). The median duration of each study was ~2 years.

The incidence and type of adverse events (AEs) reported in SPI-611 and SPI-612 was similar for both treatment groups. Regardless of treatment group, approximately 80% of patients in each study experienced at least one treatment-emergent AE (TEAE); most TEAEs (70% to 80%) were of Grade 1 or Grade 2 severity. The most common TEAEs (occurring in approximately 10% to 20% of patients in either treatment group in either study) were dysuria, urinary tract infection, hematuria, and pollakiuria with less common TEAEs (5% to 10% of patients) being micturition urgency, bladder pain, urinary retention, procedural pain and bladder spasm.

Few patients (10% to 13%) had TEAEs the investigator considered treatment related with the incidence of these AEs being similar between Qapzola and placebo. The most common treatment-related AEs (occurring in 1% to 5% of patients) were dysuria, bladder spasm, micturition urgency, bladder pain, hematuria, urinary tract infection, and pollakiuria.

Approximately 25% of patients in SPI-611 and SPI-612 reported a serious adverse event (SAE), with the incidence and types of SAEs reported being similar between studies and between treatment groups. The most common SAEs (in <3% of patients) were congestive cardiac failure, hematuria, urinary retention, atrial fibrillation, chronic obstructive pulmonary disease, pneumonia, knee arthroplasty, and coronary artery disease, most of which may be expected in an elderly population. Two patients experienced SAEs that were considered to be possibly related to Qapzola. Both SAEs started on the day of study drug instillation, and both resolved: one patient had Grade 3 hematuria and recovered within 3 days, the other had Grade 3 acute renal failure and recovered within 18 days. Another patient who received Qapzola died of acute renal failure 624 days after Qapzola treatment; the event was assessed as not related to study treatment. Hematuria is a common presenting sign of NMIBC [5, 13] and is an expected consequence of the TURBT procedure.

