5.3.2 Treatment Period: Visit 1 (Day 1)

If the screening assessments for the physical examination, hematology, chemistry, urine dipstick were performed within 3 days (72 hours) prior to Day 1/TURBT, these assessments do not need to be repeated at the Day 1 Visit.

- Vital signs (temperature, blood pressure, and heart rate)
- Complete blood count
- Chemistry
- Randomization
- Urine dipstick just prior to drug instillation
- TURBT and packaging of pathology specimens to be sent to local pathology
- Visual inspection for gross hematuria post-TURBT but prior to drug instillation
- Qapzola or placebo administration
- Concomitant Medications
- Adverse events using NCI CTCAE Version 4.03

5.3.3 Safety Follow-up Visit: Visit 2 (Day 35 [±5 days] post-TURBT (non-Target patient population) or Visit 3 (Month 3 Follow-up Visit) (Target patient population)

- Vital signs (temperature, blood pressure, and heart rate)
- Physical examination
- Complete blood count
- Chemistry
- Urine dipstick
- Adverse events using NCI CTCAE Version 4.03
- Concomitant medications

5.3.4 Long-Term Follow-up Visits - Visits 3 through 10 (First 2 Years: Every 3 months [±30 days] Post-TURBT) and Visits 11 through 16 (Years 3-5: Every 6 months [±60 days])

- Physical exam (required at Month 3 Follow-up Visit, as needed thereafter)
- Vital signs (temperature, blood pressure, and heart rate) (required at Month 3 Follow-up Visit, as needed thereafter)
- Urine dip stick prior to cystoscopy
- Complete blood count (Month 3 Follow-up Visit only)
- Chemistry (Month 3 Follow-up Visit only)
- Urine cytology
- Cystoscopy
- Only AEs related to study procedures will be recorded until the End-of-Study
- Concomitant medications (Intravesical treatment only)

- TURBT and packaging of pathology specimens to be sent to local pathology (if necessary)

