7.3.1 Recording of Adverse Events

From the time the study Informed Consent is signed through the day of study drug administration, only SAEs that are related to study procedures are to be recorded. For all non-Target population patients, all adverse events from the time of study drug administration until Day 35 (± 5 days) post-TURBT will be recorded. For Target population patients, all adverse events will be recorded from the time of study drug administration until the 3-month Follow-up Visit. Only AEs related to study procedures and deaths will be recorded from the 3 month visit until a recurrence or the remainder of the follow-up period, whichever comes first.

All AEs should include resolution at the End-of-Study for a patient. The following conventions should be followed when patient completes or discontinues from the study

- If a patient dies, the date of death should be the date of AE stop for all ongoing AEs at the time of death.
- If a patient discontinues study drug due to an AE(s), the outcome of the AE is to be followed for 35 days (± 5 days) from the date of discontinuation or until the AE has returned to Grade ≤ 1 or returned to baseline conditions for the patient.

The status of the AE and the date of last contact with the patient will be captured. If the AE has not returned to Grade ≤ 1 or to Baseline conditions for the patient by the End-of-Study, the AE stop date should be left as ongoing.

All AEs will be classified by intensity/severity ([Section 7.3.2](#)), relationship to study drug ([Section 7.5](#)), and as serious or nonserious ([Section 7.7](#)).

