9.4.2 Safety Monitoring

The clinical drug safety of study treatment will be continuously evaluated by the study Medical Monitor or designee on an ongoing basis during the course of this clinical study. All SAEs related to study treatment in this study and all other ongoing clinical studies with study treatment will be processed in compliance with current regulatory guidelines by Spectrum's Pharmacovigilance Department. This processing will include a formal assessment of each SAE by drug safety. An Independent Data Monitoring Committee (IDMC) will review the unblinded safety data from the first 30 patients to verify that the 8 mg/50 mL dose is safe. In addition, a cumulative review of all SAEs from all sources will be assessed periodically.

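### After Month 3 the recording rules name study procedures but not study drug, so a late non-fatal drug-related AE or SAE has no specific recording route

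*Protocol*

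**What the plan says.** Protocol 5.4.10 divides AE recording into periods:

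- From consent "through the day of study drug administration, only SAEs that are related to study procedures are to be recorded".
- For non-Target patients, "all adverse events from the time of study drug administration until Day 35 (± 5 days) post-TURBT will be recorded".
- The Target group has a longer period of full recording: "For Target population patients, all adverse events will be recorded from the time of study drug administration until the 3-month Follow-up Visit".
- Then "Only deaths and AEs related to study procedures will be recorded from the 3 month visit until the End-of-Study".

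The synopsis and 7.2 repeat this scheme. Section 7.3.1 does so with a different end point: "Only AEs related to study procedures and deaths will be recorded from the 3 month visit until a recurrence", or for the rest of follow-up if that is shorter. The visit list in 5.3.4 has "Only AEs related to study procedures will be recorded until the End-of-Study" and does not mention deaths. Schedule footnote j also has the late limit.

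For SAEs, 7.7.1 records everything from first dose to Day 35 (± 5) and only procedure-related events after that.

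Other text is wider. Section 7.1 makes the investigator responsible for reporting every AE and SAE seen during the study, whatever its relationship to study drug. The opening of 5.4.10 has patients asked about AEs at every visit and the answers put on the CRF. Section 9.4.2 begins "All SAEs related to study treatment in this study" and says that these will be processed.

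Treatment-related AEs are a safety endpoint in the protocol synopsis and in SAP 3.4.2. SAP 7.3.2 takes the investigator's relatedness judgement for all AEs.

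**The concern.** The late-period filter is by cause, and the only cause it admits is a study procedure. Suppose that in month 8 an investigator judges a bladder or renal event possibly due to the instilled drug and not to a cystoscopy. The specific rules do not tell the site to record it, even if it is serious. Sections 7.1 and 9.4.2 assume that it will be reported and processed.

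This matters because safety is the only objective left in the SAP (2.1). The dose is 8 mg in 50 mL, whereas the two earlier Phase 3 studies used 4 mg in 40 mL (1.3.1, 1.4), so their safety record does not cover it directly. The planned committee review of safety is limited to the first 30 patients. Those earlier studies described AEs over about two years and gave a causality judgement on a death 624 days after treatment (1.3.2). Here a death at that time would still be recorded. A non-fatal event attributed to the drug would not. A report showing no late drug-related events would then reflect the rule and not an observation.

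**Working it through.** The plan gives no figure to reproduce. The check sets the recording windows side by side and then does the day arithmetic.

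**1. What is recorded after dosing**

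| Source | Full recording until | Recorded after that |
|---|---|---|
| Synopsis, 5.4.10, 7.2, 7.3.1 (Target) | Month 3 visit | Procedure-related AEs, deaths |
| 5.3.4 (visit list) | not stated | Procedure-related AEs |
| Footnote j | 35 days after dosing | From Month 3: procedure-related AEs, deaths |
| 7.7.1 (SAEs) | Day 35 (± 5) | Procedure-related SAEs |
| 7.1 (general duty) | no limit | All AEs and SAEs, any relationship |

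No row but the last admits a late non-fatal event because it is attributed to study drug.

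**2. Could the instillation count as a study procedure?** The documents do not define the term. The nearest text, in 7.2, speaks of protocol-mandated invasive procedures and does not say whether the instillation is one. Reading it in would narrow the gap, but a site cannot be expected to infer this.

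**3. Does the late rule reduce the treatment-emergent tables?** Inputs: the treatment-emergent window is 35 days (7.2, SAP 7.3.1), the causality window is 35 ± 5 days (7.5), and the Month 3 visit has a ± 30 day window. Assumption: 3 months = 91 days.

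- Latest close of the causality window: 35 + 5 = Day 40.
- Earliest Month 3 visit: 91 − 30 = Day 61.
- Margin over the causality window: 61 − 40 = 21 days.
- Margin over the treatment-emergent window: 61 − 35 = 26 days.

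For Target patients, who are the only ones followed long-term, the post-Month-3 rule removes nothing from either window.

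**4. How long is the uncovered period?** Over the first 24 months it is 24 − 3 = 21 months, and 21/24 = 87.5%. SAP 3.3 states that no patient was followed beyond 24 months, and follow-up also stops at recurrence, so this is an upper bound per patient.

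**5. SAEs.** Between Day 35 (± 5) and Month 3, 5.4.10 records all AEs in Target patients but 7.7.1 records only procedure-related SAEs, so the two conflict. After Month 3 both exclude a non-fatal SAE attributed only to the drug.

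**6. Day 1.** The restricted period runs through the day of dosing in 5.4.10 and until Day 1 in 7.7.1, while full recording starts at the time of dosing. The overlap is the hours between instillation and the end of that day. Section 5.4.10, 7.7.1 and footnote j all order full recording from dosing, and before instillation no drug-related event can exist.

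**The case against.** The best defence is that the design is deliberate. The drug is given once, held for 60 minutes and drained. The protocol ends both the treatment-emergent window and causality assessment at about Day 35, and step 3 shows that full recording in Target patients outlasts both. The overall AE summary in SAP 7.3, including its treatment-related rows, is framed as a treatment-emergent table. In addition, 7.1 and the opening of 5.4.10 do require reporting, 9.4.2 sets no collection window, and the promise in 7.7.1 to follow treatment-related SAEs to resolution fits events that began inside the window.

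Much of this stands. The main tables are intact, and few late drug-related events should be expected. The 87.5% is a share of time and says nothing about the share of events lost. But 7.1 does not close the gap: it contradicts the specific rules, and a site completing the CRF will follow the specific rule. The treatment-related endpoint is listed apart from treatment-emergent AEs and has no time limit of its own. The causality limit in 7.5 belongs to the same gap and does not justify it.

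A reader might go further and infer that drug-related events on the dosing day are also filtered out, citing the two earlier SAEs judged possibly related to the drug: "Both SAEs started on the day of study drug instillation". The documents do not support that. The sentences next to the restrictive one record everything from dosing, as do 7.7.1 and footnote j. Events of that kind starting after instillation would be recorded here, so those two cases show no loss. Day 1 has a wording overlap only.

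**Conclusion.** The point holds for the late period. After Month 3, and for SAEs under 7.7.1 after Day 35 (± 5), a non-fatal event attributed to study drug but not to a procedure falls outside every specific recording rule, in conflict with 7.1 and with what 9.4.2 presupposes. Deaths are still recorded, although 5.3.4 leaves them out.

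The loss is confined to late drug-related events and matters most for SAEs. It should be small in number, and it does not touch the 35-day tables. This rests on three assumptions: that a month-3 visit is nominally Day 91, that the instillation is not itself read as a study procedure, and, as a judgement and not a figure in the documents, that late drug effects after one instillation are uncommon. Correcting the text is worthwhile because the cost is low and safety is the sole remaining objective.

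**What to change.** - **Late rule.** In the synopsis, 5.3.4, 5.4.10, 7.2, 7.3.1, 7.7.1 and footnote j, record in the late period *AEs and SAEs related to study drug or study procedures, and deaths*. Make the SAE period in 7.7.1 agree with the AE period in 5.4.10.
- **7.1.** Reconcile the general reporting duty with the specific rules, so that a site has one instruction.
- **7.5.** Extend causality assessment to any event recorded under the late rule. Otherwise sites would record drug-related events for which no relatedness judgement is required after about Day 40.
- **SAP.** State whether the treatment-related summaries cover events after the 35-day window or whether these are listed separately.
- **If data collection is complete.** State in the SAP or report that non-fatal drug-related AEs were not systematically ascertained after Month 3, nor such SAEs after Day 35, so that their absence is not read as evidence of safety.
- **Wording clean-up.** Use the start of instillation as the single Day 1 boundary wherever the text now uses the day of administration or Day 1.

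The cost is one set of text changes in the protocol and CRF guidance, a few extra late records and the causality judgements that go with them. No visit or test is added.

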5.4.11 Concomitant Medications

All medications administered from the time Informed Consent is signed until 35 days post TURBT will be recorded on the CRF. After 35 days, until patient discontinues from study, only additional treatment for NMIBC are to be recorded. Start and stop dates and reasons for medication use will be noted.

6 STUDY DRUG AND PHARMACEUTICAL INFORMATION

6.1 Qapzola and Placebo

Qapzola and placebo will be supplied by Spectrum.

6.1.1 Composition of Qapzola

Qapzola for intravesical instillation is a sterile, non-pyrogenic, lyophilized product supplied in two 10 mL clear glass vials. Each vial contains 4.6 mg apaziquone, 57.9 mg mannitol, and 5.8 mg sodium bicarbonate. After reconstitution, Qapzola has a reddish appearance similar to that of cranberry juice.

6.1.2 Composition of Placebo

Matching placebo containing 12 mg FD&C red #40, 15 mg sodium chloride, and 10 mg mannitol is supplied in identical appearing vials. Reconstitution and instillation procedures for placebo are the same as for Qapzola.

6.1.3 Composition of Diluent for Qapzola and Placebo

The diluent for Qapzola is a sterile solution supplied in a two 50 mL clear Type I glass vials. Each vial contains 41.2 mL of the diluent containing sodium bicarbonate, propylene glycol, disodium EDTA, and sterile water for injection.

The diluent for placebo is a sterile solution supplied in a two 50 mL clear Type I glass vials. Each vial contains 41.2 mL of the diluent containing 0.9% sodium chloride in sterile water for injection.

6.1.4 Shipping and Storage of Study Drug

Study drug is shipped on cool packs in insulated containers, and should be stored in a secure area with limited access. Study drug is to be refrigerated (approximately 2°C to 8°C) in a secure area and should be protected from direct light. Diluent for study drug may be refrigerated or stored at room temperature.

6.2 Dose, Route of Administration, and Schedule of Study Drug

6.2.1 Dose and Route of Administration of Study Drug

Randomized patients will receive either Qapzola 8 mg in 50 mL of dose solution or matching placebo. Reconstitution and dose preparation procedures are outlined in the Pharmacy Manual. The 50 mL dose solution of study drug is to be instilled into the bladder via an indwelling 100% Silicone Foley catheter, where it is to be retained for 60 ± 5 minutes.

6.2.2 Schedule of Study Drug Administration

A single dose of study drug on Day 1 is to be administered at 60 ± 30 minutes post-TURBT. Within the administration window (60 ± 30 minutes post TURBT), study drug administration should be delayed to allow for resolution of significant bleeding. Patients not candidates for post-operative intravesical chemotherapy after from TURBT (ie, extensive resection, bladder perforation, ongoing bleeding) should not receive study drug.

6.2.2.1 Preparation of Study Drug

Preparation of study drug dose solution should follow directions as described in the Pharmacy Manual. Equipment needed: Drug kit (Two 4.6 mg vials of Qapzola or placebo and two vials of Diluent), one 50 mL or 60 mL Luer-lok syringe, one 10 mL syringe with 0.2 mL marking, one 5-10 mL syringe, 18 gauge needle, protective clothing.

If study drug is reconstituted, and not used within 2 hours, it must be discarded; resupply of new study drug kits may not always be possible in a reasonable time. Therefore, patient eligibility should be confirmed prior to drug reconstitution.

6.2.2.2 Instillation of Study Drug

Following drainage, study drug is to be instilled into the bladder via a 100% Silicone Foley catheter at 60 ± 30 minutes post-TURBT. Adequate hemostasis should be obtained, and the urine should appear visually clear (No macroscopic evidence of bleeding) before study drug instillation. Within the administration window (60 ± 30 minutes post TURBT), study drug administration should be delayed to allow for resolution of significant bleeding. Patients with significant complications from TURBT (ie, bladder perforation, ongoing bleeding) should not receive study drug. The bladder should be emptied before instilling the study drug. The 50 mL of the study drug should be slowly instilled into the bladder taking care not to introduce air. When instillation is complete, the Foley catheter should be clamped for 60 minutes (± 5 minutes).

If during the retention period, there is any leakage around the catheter, the amount of study drug leaked should be estimated and recorded. After 60 minutes (± 5 minutes) of retention, the bladder contents should be drained and the drained bladder contents disposed of according to institutional policy. The institution's routine guidelines for the postoperative care should be followed.

No diuretics are allowed prior to instillation on the study drug instillation days. Study drug should not be instilled if a subclinical or clinical bladder perforation is suspected.

6.3 Disposal of Study Drug

At the end of the 60 ± 5 minutes period of retention, study drug should be carefully drained/voided into a suitable container, and disposed of according to the institution's policies for disposal of hazardous waste.

6.4 Product Accountability

The site and/or the pharmacy must maintain accurate accounting of investigational product. During the study, the following information must be recorded:

- Date of receipt, quantity and identification of the product received from the Sponsor.
- ID number of the patient to whom the product is dispensed.
- The date(s) and quantity of the product dispensed.
- Dates and quantity of product returned, lost or accidentally or deliberately destroyed.

Accountability Records will be provided by the Sponsor. They must be kept current and must be readily available for inspection.

The Investigator should not return clinical study materials to the Sponsor unless specifically instructed to do so by the Sponsor. All used vials of study drug and diluent should be destroyed per the institution's policy.

All expired vials of study drug and diluent should be retained. The Clinical Research Associate (CRA) will periodically conduct an accountability of the expired study drug and diluent and authorize their destruction. If the participating pharmacy is prohibited by institutional policy from retaining expired vials, the investigational pharmacist will then be responsible for documenting the destruction of the vials.

6.5 Treatment Blinding Procedures

This study is double-blind with respect to treatment assignment; all study participants (ie, subject, study staff including the physician, and all non-study individuals) and the Sponsor remain blinded until the study is complete and unblinded. An independent data monitoring committee (IDMC) will be established to review safety data for the first 30 treated patients in the study. The IDMC will also conduct the futility analysis of the unblinded data as described in [Section 8.1](#). The details for the IDMC will be provided in a separate Charter. An IWRS will be set up with appropriate access structure in order to keep the above study team blinded. Pharmacy will have access to the IWRS to get the treatment allocation.

The patients enrolled in this study will be randomized in a 2:1 ratio to either:

- **Arm 1:** one instillation of 8 mg Qapzola
- **Arm 2:** one instillation of placebo

In the case of a significant safety concern, a patient's treatment may be unblinded. The Investigator should first contact the Medical Monitor immediately to discuss and agree on the merits and need for unblinding a patient's treatment. The reasons and rationale for breaking the treatment blind will be documented in writing and maintained in the study file.

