4.2 Exclusion Criteria

1. Patient has malignancy or life-threatening systemic disease or a history of advanced, serious, life-threatening malignancy/disease within the last 5 years, except very low-risk prostate cancer
2. Patient has used any investigational drugs, biologics (vaccines, antibodies), or devices within 30 days prior to study treatment or has plans to use any of these during the course of the study
3. Patient has received any pelvic radiotherapy (including external beam and/or brachytherapy)
4. Patient has a history of allergy to red color food dye or any other component of Qapzola, placebo, or their diluents
5. Patient has had a surgical procedure 4 weeks prior to TURBT or will have other surgical procedures performed at the time of TURBT or within 4 weeks after TURBT
6. Patient has any unstable or uncontrolled medical condition that would make it potentially unsafe to undergo TURBT including a previous stroke or myocardial infarction within 6 months
7. Patient has an active uncontrolled infection, including a urinary tract infection, underlying medical condition, or other serious illness that would impair the ability of the patient to receive study treatment or undergo study procedures
8. Patient has a bleeding disorder or a screening platelet count $<100 \times 10^9/L$, or requires continuous anticoagulation or bridging anticoagulation during the procedure
9. Patient has a hemoglobin value <10 g/dL at Screening
10. Patient has ever had confirmed extravesical urothelial disease (upper tract and urethral including prostatic urethral)

11. Patient with a history of previous bladder cancer:
 - High-Risk NMIBC as classified per the 2016 AUA Guidelines
 - Bladder cancer that was muscle invasive or positive for lymph node or distant metastasis
12. Patient has received any previous intravesical therapy for bladder cancer- chemotherapy, immunotherapy, or previous exposure to Qapzola in the last 3 years
13. Patient has a tumor in the bladder diverticulum
14. Patient has a history of interstitial cystitis
15. Patient is pregnant or breast-feeding

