8.2 Method of Treatment Assignment, Randomization

Patients who meet all eligibility criteria may be considered for randomization. Eligibility of all patients will be reviewed and approved for randomization by the Sponsor's Medical Monitor, or designee. Patients approved for randomization will be randomized 2:1 to receive one instillation of 8 mg Qapzola or one instillation of placebo.

The randomization plan will use a permuted block design and will not be stratified. Study drug kits will contain either vials of Qapzola, or placebo and will be patient specific. Patients will be randomized within a center. Patient numbers will be assigned sequentially at each site.

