9 ADMINISTRATIVE PROCEDURES AND STUDY MANAGEMENT

9.1 Investigator Responsibilities

9.1.1 Good Clinical Practice

It is the responsibility of the Principal Investigator to oversee the safety of the patients at their site. The Investigator will ensure that this study is conducted in full compliance with the principles of the “Declaration of Helsinki” (as amended in Tokyo, Venice, Hong Kong, and South Africa), ICH guidelines, or with the laws and regulations of the country in which the research is conducted. By signing the US Form FDA 1572, “Statement of Investigator”, the Investigator commits to adhere to applicable sections of the US CFR parts 50 “Protection of Human Patients”, 54 “Financial Disclosure by Clinical Investigators”, 56 “Institutional Review Boards”, and 312 subpart D “Responsibilities of Sponsors and Investigators”. All Investigators will ensure adherence to ICH guidelines for GCP and Clinical Safety Data Management.

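### Protocol section 6.5 has no emergency route for unblinding one patient without first seeking the sponsor Medical Monitor's agreement, and it names no final decision-maker

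*Protocol*

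**What the plan says.** Protocol section 6.5 sets the trigger for individual unblinding: "In the case of a significant safety concern, a patient's treatment may be unblinded". It then sets the order of steps: "The Investigator should first contact the Medical Monitor immediately to discuss and agree on the merits and need for unblinding a patient's treatment". After that it asks for a record: "The reasons and rationale for breaking the treatment blind will be documented in writing and maintained in the study file".

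Section 8.2 shows whose Medical Monitor this is: "Eligibility of all patients will be reviewed and approved for randomization by the Sponsor's Medical Monitor, or designee".

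On access, section 6.5 keeps the patient, the study staff including the physician, and the sponsor blinded, and says the IWRS will be configured to achieve this. One group is given the allocation: "Pharmacy will have access to the IWRS to get the treatment allocation".

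On responsibility, section 9.1.1 says: "It is the responsibility of the Principal Investigator to oversee the safety of the patients at their site". Section 7.7.1 tells the investigator to treat a serious adverse event as needed, and does not mention the code.

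The protocol's other references to unblinded data concern the IDMC's safety and futility reviews. The SAP has no procedure for breaking the blind.

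**The concern.** The investigator answers for the patient's safety but has no described way to learn what the patient received without first going to someone outside the site. The wording asks for agreement, which is more than notification, and it covers every significant safety concern alike. An acute emergency and a query that can wait a day follow the same path.

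If the monitor is reached at once and agrees, little is lost. If the monitor cannot be reached, or takes a different view, the text does not tell the investigator what to do next. Someone who follows the written order will wait.

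The arms do differ in what is put into the bladder. Qapzola is an alkylating agent (section 1.2), and its diluent contains propylene glycol and disodium EDTA (section 6.1.3). The other arm is described this way: "Matching placebo containing 12 mg FD&C red #40, 15 mg sodium chloride, and 10 mg mannitol is supplied in identical appearing vials". The protocol treats sensitivity to these constituents as a hazard by excluding anyone for whom this holds: "Patient has a history of allergy to red color food dye or any other component of Qapzola, placebo, or their diluents". So it is conceivable that a treating physician would want the allocation quickly.

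**Working it through.** No arithmetic bears on the main point. The check is to ask what an emergency rule has to settle and whether either document settles it.

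| Question | What the documents give |
|---|---|
| When may one patient be unblinded? | For a significant safety concern (protocol 6.5) |
| What comes first? | Contact with the sponsor's Medical Monitor, to discuss and agree (6.5, 8.2) |
| How fast? | The contact is to be immediate (6.5) |
| Is an emergency treated differently? | Not stated |
| What if the monitor is unreachable? | Not stated |
| What if the two disagree? | Not stated |
| Who has the final decision? | Not stated |
| Who can see the allocation? | Pharmacy, through the IWRS (6.5) |
| Does the investigator have emergency access? | None described; the physician is among those to be kept blinded (6.5) |
| What is recorded? | Reasons and rationale, in writing (6.5) |

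Three steps follow.

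1. The requirement for immediate contact governs how soon the call is made. It does not remove the agreement step.
2. The duties in sections 7.7.1 and 9.1.1 do not carry authority to open the code, so they do not fill the gap.
3. The written record explains a code break after the event. It does not settle who may order one.

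One calculation helps with the cost of a change. Section 8.2 specifies permuted blocks, randomization within a center and a 2:1 ratio. The synopsis gives about 500 patients at about 70 centers, or 500/70 = about 7 per center. Block size is not given, so sizes of 3 and 6 are taken here as assumptions. Before any unblinding, each patient has a 2/3 chance of being on Qapzola. Suppose the site knows the block boundaries and one patient's code is broken:

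- **Block of 3 (2 Qapzola, 1 placebo).** If the patient is on placebo, the other two are certainly on Qapzola (2/2). If the patient is on Qapzola, each of the others has a chance of 1/2.
- **Block of 6 (4 Qapzola, 2 placebo).** If the patient is on placebo, each of the other five has a chance of 4/5. If on Qapzola, 3/5.

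One code break can therefore reveal something about a few neighbouring patients, and the most when blocks are short and their size is known.

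**The case against.** The text is milder than a hostile reading makes it. The verb is *should*. Sections 5.2 and 6.6 use the stronger *must not* for a true bar, on resection before randomization. A reader might infer that the sponsor holds a veto, but the protocol states none. The possibility of refusal arises only because agreement is asked for and no tie-break is given. This stands, and it limits the point to a gap in the rule.

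A reader might also infer from the differing constituents that emergency care depends on the arm. The documents do not say so. They describe no antidote and no arm-specific management. There is one instillation, drained after about an hour, so no later dose depends on the answer. Known allergy to a constituent of either arm is an exclusion, and section 6.2.2.2 bars instillation when perforation is suspected. Section 7.7.1 lets treatment of a serious adverse event proceed without the code. All this makes a need for the allocation rare; it does not show that the need cannot arise.

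Nor does the rule compromise the Medical Monitor's own blind. Section 6.5 does not say that the monitor receives the allocation, and consultation alone reveals nothing.

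Finally, the IWRS instructions, the study binder and the Pharmacy Manual were not available for this review, and an emergency code-break could be described in one of them. Section 6.5 does not refer to any of them for unblinding. This lowers certainty about practice at the sites but does not change what the protocol says.

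**Conclusion.** The point holds as a gap in a stated rule. Section 6.5 puts prior discussion and agreement with the sponsor's Medical Monitor first, with no emergency exception, no fallback and no named final decision-maker, while the physician has no described access to the code. Followed as written, it can delay treatment information for an acutely ill patient. No delayed or refused request is documented.

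The size cannot be put as a rate. It is tempting to use the two possibly related serious adverse events in the earlier pivotal studies (section 1.3.2), both of which began on the day of instillation. They do not measure this. Neither is described as needing a code break, and they occurred at 4 mg/40 mL (section 1.3.1), whereas this trial gives 8 mg/50 mL. That few patients would be affected is a judgement, based on a single instillation and the safeguards already in place.

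The conclusion assumes that no operational document supplies an emergency route. The SAP records that the study was terminated early, so the correction now matters mainly wherever this wording is used again. The change is worth making because it is cheap and improves safety.

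**What to change.** Amend section 6.5 to separate two cases.

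- **Emergency in which that patient's care needs the allocation.** The investigator holds the final decision and can break that patient's code through the IWRS, or through the unblinded pharmacy, without prior sponsor agreement. Contact with the Medical Monitor beforehand is encouraged when time allows. Otherwise the monitor is told promptly afterwards that the code was broken and why, but not the allocation.
- **Any other request.** The present discussion with the Medical Monitor can stay.

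In both cases, record the date, time, reason and the persons unblinded, in addition to the written rationale already required.

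The cost is a short rewording and an emergency role in an IWRS that already releases the allocation to pharmacy. The downside is a small added risk of unnecessary unblinding, with some inference about other patients in the same block at that center. Pathology confirmation of recurrence (section 8.5.1) limits the effect on the primary endpoint but does not abolish it, because a lesion must first be seen and biopsied at cystoscopy. Confining the new route to emergencies, and keeping the block size from the sites, holds that risk down.
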